## MATERIALS AND METHODS

This was a prospective, randomized, observational study performed in 2 months in the Delivery Room of the Department of Obstetrics and Gynecology by the Newborn Department where approximately 3,500 infants are delivered annually. Stabilization followed the NRP guidelines and is implemented by a neonatology fellow and three pediatric assistants with NRP certificates. Single, term, appropriate for gestational age (AGA) babies who did not need resuscitation and babies in whom skin-to-skin contact cannot be applied were included in the study. Vaginal births were not included, only babies born with cesarean sectio (CS) and couldnot not exposed to early skin-to-skin contact were included.

---

Spinal anesthesia was used for the mothers for CS, mother was not given oxygen therapy until the baby came out. Parents were informed of the study prior to birth and written consent was obtained from those who were willing to participate. The babies were randomized by opening of envelopes containing positional codes and were placed supine, on the right or left side, or prone (15/group).

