### **3.Cerebral oxygenation:**

Near-infrared spectroscopy (NIRS), which measures tissue oxygenation noninvasively, was used to evaluate cerebral oxygenation; the mean values at 5th and 10th min were recorded using a Covidien INVOS 5100C instrument. The cerebral regional cerebral oxygen saturation (rScO2) is the ratio of cerebral oxygenated hemoglobin (CHbO2) to the total oxygen bound to cerebral hemoglobin (CHb) and CHbO2 (rScO2 = CHbO2/CHb + CHbO2) . The rScO2 is the mean oxygen saturation of cerebral arterial, venule, and capillary blood; the venule data is predominate . Infrared light reveals the extent of saturation of the so-called watershed zone (a mixture of 33% arterial and 67% venous blood at a depth of 1-1,5 cm) . The NIRS probe was placed on both sides of the frontal lobe; the probe was cleaned before placement. The first measured value served as the basal value; rScO2 changes were then recorded at 2-s intervals to 60 s and the mean calculated. The cerebral rScO2 is normally 50-80, but may vary by 10-20% at any time . A decrease >20% for patients with a basal cerebral rScO2 value >50 and a decrease >15% for those with a basal cerebral rScO2 <50 indicate cerebral ischemia . Data were captured at 0.1 Hz and collected for 10 min, after application in each position consequently. Cerebral fractional oxygen extraction (cFOE) was calculated for 5th and 10th min average as ( (SpO2-rScO2)/SpO2 ) (SpO2: pulse oximetry oxygen saturation) for each position, which reflects the balance between oxygen delivery and consumption in the tissue .

An infant/pediatric sensor (Covidien INVOS 5100C) costs between \$110 and \$140 each. No outside funding was used for the budget in this study. Within the budget and time period, the maximum number of patients enrolled in the study.

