#### **4. Sample Size:**

In the investigators' center, monthly birth rate is 300 and since our hospital is the largest perinatology center in our region; the number of births with maternal and neonatal problems is high. When the investigators evaluated our records for the number of infants who were born  $> 37$  GA with CS under spinal anesthesia and did not require any resuscitation efforts; the number was approximately 15 per month. ( $P=0.05$ ) with a 2-sided a error of 5% and power of 80%, a total sample size of 37 total was required.

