### **Statistical Analyses:**

SPSS 25.0 (IBM Corporation, Armonk, New York, United States) and PAST 3 (Hammer, Ø., Harper, D.A.T., Ryan, P.D. 2001. Paleontological statistics) programs were used in the analysis of the variables. The conformity of univariate data to normal distribution was evaluated with the Shapiro-Wilk francia test, while homogeneity of variance was evaluated with the Levene test. Mardia for the conformity of multivariate data to normal distribution; while the (Dornik and Hansen omnibus) test was used, the Box-M test was used for variance homogeneity. In the comparison of more than two groups according to quantitative data, Fisher's Least Significant Difference (LSD) tests were used for One-Way Anova post hoc analysis, one of the parametric methods, Kruskal-Wallis H Test, which is one of the nonparametric tests, was used with the results of Monte Carlo simulation technique, and Dunn's Test was used for Post Hoc analyses. The Paired-Samples T test was tested using Bootstrap results, while the Wilcoxon Signed Ranks Test was tested using the monte carlo simulation method to compare two replicate measurements of dependent quantitative variables with each other. While Friedman's Two-Way test was tested using the monte carlo simulation method to test the variables with more than two repeated measurements and to examine the interaction according to the groups, the General Linear Model-Repeated Anova test from parametric methods was used, and the LSD test was used for Post Hoc analyses. In the comparison of categorical variables with each other, Fisher-Freeman-Holton test was tested with Monte Carlo Simulation technique. While quantitative variables were expressed as mean (standard deviation) and Median (Percentile 25 / Percentile 75) in the tables, categorical variables were shown as n (%). The variables were analyzed at 95% confidence level, and a p value less than 0.05 was considered significant.

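### The bootstrap behind the paired t test is not specified; a non-studentised one would run at about 8% rather than 5% within positions of 15 infants, and about 6% if pooled

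*Combined protocol and SAP*

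**What the plan says.** The Statistical Analyses section gives two methods for comparing two repeated measurements in the same infant. For the parametric one it says "The Paired-Samples T test was tested using Bootstrap results". The other is the Wilcoxon signed ranks test with Monte Carlo simulation. Their shared purpose is "to compare two replicate measurements of dependent quantitative variables with each other". The section closes with "The variables were analyzed at 95% confidence level, and a p value less than 0.05 was considered significant".

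On normality it says "The conformity of univariate data to normal distribution was evaluated with the Shapiro-Wilk francia test". No sentence makes the choice between the paired t test and Wilcoxon depend on that check, although the pairing suggests it. The software is "SPSS 25.0 (IBM Corporation, Armonk, New York, United States) and PAST 3". The bootstrap type, the number of resamples and the interval method are not given.

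On group size, Materials and Methods says that infants "were placed supine, on the right or left side, or prone (15/group". This can be read as three positions (45 infants) or four (60).

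The Statistical Analyses section does not name the outcomes for the paired test. Under Cerebral oxygenation, rScO2 is recorded at exactly two times: "the mean values at 5 th and 10 th min were recorded using a Covidien INVOS 5100C instrument". cFOE is calculated at the same two times. Apgar score also has two times (1 and 5 minutes). Heart rate, saturation and perfusion index have three.

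**The concern.** If the paired t test is the branch for normal-looking data, the ordinary version already has the stated 5% error and 95% coverage when the differences are normal, at any sample size. A bootstrap of the mean difference that is not studentised loses two things in a small sample. Resampling the n observed differences understates the standard error by a factor of sqrt((n−1)/n). It also drops the allowance that the t distribution makes for an estimated standard deviation. Both push towards too many significant results and intervals that are too narrow.

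At stake are statements that an outcome changed between two times, such as cerebral oxygenation from 5 to 10 minutes. A reader told 5% and 95% could not tell from the plan whether those levels apply.

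**Working it through.** **Inputs.** Two-sided alpha of 5% (Sample Size: "with a 2-sided a error of 5% and power of 80%, a total sample size of 37 total was required"); 95% confidence (Statistical Analyses); n = 15 within a position, or 3 × 15 = 45 or 4 × 15 = 60 if pooled (Materials and Methods). The bootstrap type is not stated, so each common type was tried. The total of 37 cannot be reproduced, because no effect size, standard deviation, endpoint or test is given. It plays no part below. The plan's figures that matter here are the 5% and the 95%.

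**Closed form.** With s the standard deviation of the differences, the bootstrap standard error of their mean is s × sqrt((n−1)/n) / sqrt(n). A non-studentised bootstrap therefore rejects at about |t| > 1.96 × sqrt((n−1)/n). With normal differences t has n−1 degrees of freedom.

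- n = 15: threshold 1.96 × sqrt(14/15) = 1.893; P(|t14| > 1.893) = 7.9%, coverage 92.1%.
- n = 45: threshold 1.96 × sqrt(44/45) = 1.938; 5.9%, coverage 94.1%.
- n = 60: threshold 1.96 × sqrt(59/60) = 1.944; 5.7%, coverage 94.3%.

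The correct threshold at n = 15 is 2.145, so the t interval is 2.145 / 1.893 = 1.13 times as wide.

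**Simulation with no true change and normal differences** (1,000 resamples; 20,000 runs at n = 15, 6,000 at n = 45 and at n = 60). False-positive rates:

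| Method | n = 15 | n = 45 | n = 60 |
|---|---|---|---|
| Ordinary paired t | 4.8% | 4.9% | 5.1% |
| Centred bootstrap p on the mean | 7.8% | 5.8% | 5.7% |
| Percentile interval | 8.3% | 6.0% | 5.9% |
| BCa interval | 8.4% | 6.1% | 6.0% |
| Studentised bootstrap | 4.2% | 4.8% | 4.9% |

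The Monte Carlo standard error near 8% at n = 15 is sqrt(0.08 × 0.92 / 20,000) = 0.2 percentage points.

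**Keeping only samples that pass Shapiro-Wilk at n = 15:**

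| True differences | Ordinary t | Centred p | Percentile | BCa | Studentised |
|---|---|---|---|---|---|
| Normal | 4.9% | 7.8% | 8.3% | 8.4% | 4.4% |
| Skewed (gamma, shape 4) | 6.9% | 10.1% | 10.1% | 9.9% | 6.1% |
| Heavy-tailed (t, 5 df) | 4.8% | 7.7% | 8.4% | 9.7% | 4.3% |
| Uniform | 4.4% | 7.1% | 6.7% | 5.4% | 3.7% |

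Screening for normality does not remove the inflation. The ordinary t test has a lower error than each non-studentised bootstrap in every row. The gap is small only for BCa with uniform differences.

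**The case against.** The strongest reply is that the plan never commits to a bootstrap that fails. A reader might infer that the trial's paired tests do run at 8%. The documents do not support that: a studentised bootstrap fits the same sentence and shows no inflation. Naming the software does not settle which option was used. This stands, and so the 8% is conditional.

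The level of analysis is open too. Nothing says that the paired test is run separately in each position. Pooled, the error is about 6%, which is close to nominal. Within-position testing is a natural reading, since cFOE is described as calculated for each position, but it is a reading.

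A reader might also take the ordinary t test to be exact in this branch. It is exact only for truly normal differences, and passing Shapiro-Wilk at n = 15 does not show that: with skewed differences that passed, it ran at 6.9%. That limits the word exact but does not favour the bootstrap, since the non-studentised versions ran at about 10% in the same samples.

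It is tempting to multiply up over positions. If 7.9% applied in each, the chance of at least one false change per outcome would be 1 − 0.921³ = 21.9% for three positions, or 1 − 0.921⁴ = 28.0% for four. But 1 − 0.95³ = 14.3% and 1 − 0.95⁴ = 18.5% arise from uncorrected multiplicity alone. The bootstrap adds about 8 to 10 points, and the rest would remain after the fix.

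Finally, a reader might infer that the comparison of positions is compromised. It is not. Positions are compared by one-way ANOVA or Kruskal-Wallis, and position by time through the repeated-measures general linear model. None of these is said to use the bootstrap.

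**Conclusion.** The point holds in conditional form and is minor. The plan rests the paired t test on a bootstrap that it does not specify, at a level of analysis that it does not state. If the bootstrap is non-studentised and run within positions of 15, the excess over the stated 5% is about 3 percentage points with normal differences, with a matching loss of coverage. If pooled over 45 or 60, the excess is about 1 point or less. If studentised, there is none.

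This is more than missing detail, because the ordinary paired t test had the lower error in every case tried and needs no such choice. The conclusion concerns within-infant change over time only. That rScO2 and cFOE are among the outcomes tested this way is inferred from their two recording times.

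**What to change.** In the Statistical Analyses section, replace the bootstrap sentence with one stating that the ordinary paired t test p value and 95% t interval are reported for two-time comparisons, and that the Wilcoxon signed ranks test is used when the paired differences fail the normality check. If a bootstrap is preferred, name the studentised (bootstrap-t) version and the number of resamples. In either case, state which outcomes the test applies to and whether it is run within each position or over all infants.

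The cost is a few lines of text and no new data. Compared with a non-studentised bootstrap, intervals at n = 15 become about 13% wider and p values slightly larger, so some borderline changes over time may no longer be called significant. The change does not address multiplicity across positions or outcomes.

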### **2. Medical records and vital parameters:**

All evaluations commenced 30 s after delivery and terminated at 10 min. For each infant, the 1st and 5th min Apgar scores were calculated by the same person, and the heart rate (HR), pulse oximetry, and perfusion index (PI) were recorded at 2nd, 5th, and 10th min using a Masimo Radical-7 pulse co-oximetry with an adhesive sensor. The probe was placed preductally (on the right wrist) and then connected to the oximetry. The fraction of inspired oxygen (FiO2) was only 0.21 ("room-air") during all the stabilization period. In line with the NRP 2015 guideline,

aspiration was not routinely performed in the delivery room; the number of times that touch stimulation was required and the tactile stimulus time were recorded. Although electrocardiography (ECG) recommended in the latest guidelines and reads heart rate much faster, pulse oximetry had to be used in our study because the relationship between position and saturation and cerebral oximetry was evaluated.

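### Friedman's test, named as written for the interaction with position, ignores position; on the non-parametric route the course of HR, SpO2 and PI has no position-by-time test

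*Combined protocol and SAP*

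**What the plan says.** Section 2 (Medical records and vital parameters) gives three readings per infant for heart rate, pulse oximetry and perfusion index: they "were recorded at 2 nd , 5 th , and 10 th min". Section 3 (Cerebral oxygenation) gives only two for rScO2: "the mean values at 5 th and 10 th min were recorded". cFOE is calculated at the same two times.

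The Statistical Analyses section plans normality checks and names parametric and non-parametric methods side by side. For repeated measurements it reads "While Friedman's Two-Way test was tested using the monte carlo simulation method" and continues directly with the purpose, "to test the variables with more than two repeated measurements and to examine the interaction according to the groups". After a comma it adds that "the General Linear Model-Repeated Anova test from parametric methods was used", with LSD post hoc.

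For comparing more than two groups, the non-parametric method is the "Kruskal-Wallis H Test, which is one of the nonparametric tests", with Monte Carlo p-values and Dunn's test post hoc. Nothing says that it is applied to changes over time. No other rank method for group by time is named.

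**The concern.** Position is the randomised factor. A natural question for a variable read at 2, 5 and 10 min is whether its course differs between positions. The sentence appears to give that question to a test that has no position input.

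If a Friedman p-value were reported as the interaction result, two errors could follow. Ordinary change in the minutes after birth could be taken for an effect of position. A real difference in course could also go unseen because opposite trends cancel. Both arise only for HR, SpO2 and PI, and only when a variable takes the non-parametric route.

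**Working it through.** **The plan's own figure.** The only computed design figure is the total of 37 in section 4 (Sample Size). It has no stated endpoint, effect size or SD, so it cannot be reproduced. This point does not depend on it.

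**What Friedman's test uses.** With N infants, k times and R_j the sum over all infants of the within-infant rank at time j,

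Q = 12 / [N k (k+1)] × Σ R_j² − 3N(k+1).

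For k = 3 this is Q = Σ R_j² / N − 12N. Position appears nowhere. The Monte Carlo null shuffles times within infant, so position is absent there too. The two ways in the test's name are infant and time. As a check, permuting the position labels in a simulated data set left Q at 19.30.

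**Two extreme cases, free of distributional assumptions.** Take N = 4 × 15 = 60.

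- Every infant rises, whatever the position: R = (60, 120, 180). Q = (3,600 + 14,400 + 32,400)/60 − 720 = 840 − 720 = 120, the largest possible value, with no position effect.
- All infants in two positions rise and all in the other two fall: each R_j = 30 × 1 + 30 × 3 = 120 at the outer times and 60 × 2 = 120 at 5 min. Q = 3 × 14,400/60 − 720 = 0, with the strongest possible interaction.

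**Simulated size.** Inputs from the documents: three times, alpha 0.05, and infants who "were placed supine, on the right or left side, or prone (15/group". That wording allows three positions (3 × 15 = 45) or four (4 × 15 = 60). Assumed, because the documents give no values: normal data, SD 1 at each time, correlation 0.5 between times. In the diverging scenarios with three positions one goes up, one stays flat and one goes down; with four, two go up and two go down. Entries are the percentage of trials with p < 0.05.

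| Scenario | Positions | Friedman | Kruskal-Wallis on 10 − 2 min change | Kruskal-Wallis at 10 min |
|---|---|---|---|---|
| No trend, no position effect | 3 or 4 | 4.5–4.8 | 4.7–4.8 | – |
| Shared rise 0.5 / 0.75 / 1.0 SD, no position effect | 3 | 69 / 98 / 99.8 | 4–5 | 3–5 (0.75 SD rise) |
| Same | 4 | 84 / 99 / 100 | 4–5 | 3–5 (0.75 SD rise) |
| Equal at 2 min, diverging to ±0.75 SD at 10 min | 3 | 2–4 | 94–95 | 94–95 |
| Same | 4 | 2–4 | >99 | >99 |
| Same divergence, courses crossing at 5 min | 3 | 2–4 | 94 | 37–39 |
| Constant ±0.75 SD from 2 min on | 3 | about 5 | about 5 | 94 |

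Ranges reflect repeat runs. Friedman's result is the same for diverging and crossing courses because adding a constant to all of an infant's readings leaves the within-infant ranks unchanged.

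**Why Kruskal-Wallis at 10 min does well in one diverging case and not in the other.** The variance of the change is 2(1 − 0.5) = 1, so the change has the same SD as a single reading. For means of −0.75, 0 and +0.75, the signal Σ n·mean² is 15 × 2 × 0.5625 = 16.9, whether it sits in the change or in the 10-min value. When courses cross at 5 min, the 10-min means are only ±0.375 and the signal falls to 15 × 2 × 0.140625 = 4.2, a quarter.

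**Second parametrisation** (between-infant SD 1, residual SD 1, 10,000 trials). A shared trend of 0.25 / 0.5 / 1.0 residual SD per step gives Friedman 41 / 95 / 100% (three positions) and 53 / 99 / 100% (four). The GLM time-by-position test stays at about 5%. With opposed trends of 0.5 per step, Friedman rejects 4.2% (three) and 3.0% (four), and the GLM interaction 88% and 99%. The parametric route is therefore not at fault.

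**The case against.** **The sentence may not mean what its comma says.** The section has other broken sentences, and Friedman for time with GLM for the interaction is a natural reading. This stands: a reader might infer that a wrong test was definitely chosen, and the documents do not settle that. On the gentler reading the fault is an omission, and the non-parametric route still has no interaction test.

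**Kruskal-Wallis already compares positions.** This also stands. A reader might infer that position effects on these variables go untested or are missed on the non-parametric route. They are not: in the diverging case with three positions, Kruskal-Wallis at 10 min does as well as the change score, and Bonferroni correction over the three times still leaves 86% power to detect a difference at some time. The shortfall is confined to courses such as crossing ones, and to the fact that separate comparisons at each time do not test whether courses differ.

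**The 70 to 100% figures are not inflated type I error for Friedman's own null.** Correct. Friedman is then rightly rejecting no change over time, and without a shared trend it holds about 5%. The rejections mislead only if read as evidence about position. The purpose clause invites that reading, but no text says that the results will be reported so.

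**Comparing Friedman verdicts obtained separately in each position would also mislead.** A reader might add this, but the documents do not describe that practice, so it is no part of the point.

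**Conclusion.** The point holds in a limited form. On either reading of the sentence, a non-normal HR, SpO2 or PI series has no named test that can show whether its course depends on position; as punctuated, the test named for that purpose is one that cannot do it. That Friedman is blind to position follows from its formula and rests on no assumption.

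The sizes do rest on assumptions (normal data, SD 1, correlation 0.5, 15 per position, three or four positions): about 70 to 100% rejection under a shared 0.5 to 1.0 SD rise with no position effect, and about 2 to 4% when courses diverge by ±0.75 SD with no average trend. The practical loss is smaller than those figures suggest, because the per-time Kruskal-Wallis tests remain. It is clearest for crossing courses.

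rScO2 and cFOE have two times and do not reach Friedman's test; the Wilcoxon signed-rank test named for two measurements likewise ignores position. The change should be made, but the point does not invalidate the analysis plan as a whole.

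**What to change.** 1. Reword the sentence so that Friedman's test, and the Wilcoxon signed-rank test for variables with two times, describe change over time only and support no conclusion about position.
2. State that Kruskal-Wallis with Dunn's test is applied at each time for differences between positions, and keep it.
3. For HR, SpO2 and PI on the non-parametric route, name one position-by-time test: either a rank-based ANOVA-type test using all three times, or the Monte Carlo Kruskal-Wallis test, permuting position labels, on each infant's change from 2 to 10 min.

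The cost is a reworded sentence and, for the second option, one computed difference per variable in software already named. No new data or infants are needed. Whether the named packages offer the ANOVA-type test should be checked.

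The change score has two drawbacks. It omits the 5-min reading. It also cannot see a position effect already present at 2 min that stays constant (about 5% rejection, against 94% for Kruskal-Wallis at each time in the ±0.75 SD case). Evaluations start 30 s after delivery, and nothing identifies the 2-min reading as a baseline taken before positioning, so this case is possible. The change score must therefore supplement the per-time comparisons and not replace them.

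### Does the plan need to say which position test decides, and whether the GLM interaction covers the two-time outcomes rScO2 and cFOE?

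*Combined protocol and SAP*

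**What the plan says.** The Statistical Analyses section assigns tests by type of data:

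- **Between positions, one measurement.** "In the comparison of more than two groups according to quantitative data", it gives one-way ANOVA with LSD, or Kruskal-Wallis with Dunn's test.
- **Two repeated measurements.** Paired t (bootstrap) or Wilcoxon (Monte Carlo). These compare times, not positions.
- **More repeats, and group interaction.** Friedman and the repeated-measures GLM share one sentence, whose scope is "to test the variables with more than two repeated measurements and to examine the interaction according to the groups". The part of it that brings in the GLM reads "to examine the interaction according to the groups, the General Linear Model-Repeated Anova test from parametric methods was used".
- **Assumption checks.** Univariate and multivariate normality, Levene and Box-M.
- **Threshold.** Throughout, "a p value less than 0.05 was considered significant".

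Section 2 (Medical records and vital parameters) records heart rate, oximetry and perfusion index at 2, 5 and 10 min. Section 3 (Cerebral oxygenation) records rScO2 and cFOE at 5 and 10 min, and adds that "The first measured value served as the basal value". Section 2, when explaining why oximetry was used in place of ECG, says that "the relationship between position and saturation and cerebral oximetry was evaluated". Allocation is by envelope; infants "were placed supine, on the right or left side, or prone (15/group"), which can be read as three groups (45 infants) or four (60).

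**The concern.** The between-position ANOVA at one time, the GLM position main effect and the GLM position-by-time interaction answer different questions. A difference between positions that stays constant from 5 to 10 min shows at each time and in the main effect, but not in the interaction. A difference that emerges between 5 and 10 min shows in the interaction and at 10 min, but not at 5 min. The available text does not say which result carries the conclusion about position.

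The sentence on the GLM adds a second doubt. If the restriction to more than two measurements applies to the GLM as well as to Friedman, the two cerebral outcomes get no interaction test, and the only tests worded for two measurements do not compare positions. Counting basal rScO2 as a time would make it a three-time outcome and move it to the other class. No nonparametric counterpart to the interaction is named.

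At stake is the error rate per outcome. If whichever test gives p<0.05 is reported as the finding, it exceeds the nominal 5%.

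**Working it through.** **The plan's own figure.** Section 4 (Sample Size) states: "with a 2-sided a error of 5% and power of 80%, a total sample size of 37 total was required". It gives no effect size, SD, outcome or test, so 37 cannot be recomputed. Solving backwards for a one-way ANOVA with N = 37 and 80% power needs Cohen's f of about 0.53 (three groups) or 0.58 (four groups). The sample-size text therefore does not reveal the deciding test. Its missing effect size is a separate matter.

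**Inputs.** From the plan: 15 per group, three or four groups, alpha 0.05, and the measurement times above. Assumed: normal data, compound symmetry, within-infant correlation ρ from 0.3 to 0.9, and for power a 1 SD difference in one position.

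**False positives with no position effect** (simulation, 40,000 trials per setting). With two times, the GLM interaction is the one-way F test on the change from 5 to 10 min. The table gives the chance that at least one of the 5 min ANOVA, the 10 min ANOVA and the interaction is significant.

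| ρ | 3 groups | 4 groups |
|---|---|---|
| 0.3 | 12.8% | 12.5% |
| 0.5 | 12.7% | 12.5% |
| 0.7 | 12.4% | 12.4% |
| 0.9 | 11.6% | 11.8% |

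Each test alone rejects in 4.8–5.2% of trials. For a three-time outcome, any of three ANOVAs or the interaction gives 12.8–16.0%.

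**Where the excess comes from.** Two independent tests would give 1 − 0.95² = 9.75%. For the correlated 5 and 10 min ANOVAs alone, the rate runs from about 7.2% at ρ = 0.9 to about 9.4% at ρ = 0.3. The interaction adds roughly 3 to 4.5 points. The share of the excess over 5% due to testing at two times (three groups) is:

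- ρ = 0.3: (9.4 − 5)/(12.8 − 5) = 4.4/7.8, or 56%
- ρ = 0.9: (7.2 − 5)/(11.6 − 5) = 2.2/6.6, or 33%

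**Power.** The noncentral F test has noncentrality λ = 15·Σ(μᵢ − μ̄)²/v. With one position shifted by 1 SD, Σ(μᵢ − μ̄)² is 2/3 for three groups and 3/4 for four, so λ = 10/v or 11.25/v. The variance v is 1 at a single time, (1+ρ)/2 for the mean of the two times, and 2(1−ρ) for the change. If the shift is present at 10 min only, the mean over the two times shifts by 0.5 SD, so its λ is a quarter as large.

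| Shift | ANOVA at one time | Main effect | Interaction |
|---|---|---|---|
| Same at 5 and 10 min | 78% | 81–94% | about 5% |
| At 10 min only | 78% (at 10 min) | 25–38% | 62% to over 99% |

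**The text set against the outcomes.** Matching the number of measurements to the test classes gives a usable mapping. Positions are compared at each time by ANOVA or Kruskal-Wallis for all five outcomes. Change within infants uses paired t or Wilcoxon for rScO2 and cFOE, and Friedman for heart rate, oximetry and perfusion index. Group interaction uses the GLM. The only open cell is whether that last line includes rScO2 and cFOE, and on either reading both outcomes still get a valid comparison of positions at 5 and at 10 min.

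**Basal rScO2.** Section 3 uses the first value as the reference for its percentage falls that indicate ischaemia, and lists only the 5 and 10 min means as recorded results. The natural reading is that it is not a third time in the model, although the text does not exclude it.

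**The case for a change.** The strongest case for a change is that the choice of test can reverse the answer. With a constant 1 SD shift, the main effect detects it in 81–94% of trials and the interaction in about 5%. The inferred mapping does not say whether the per-time ANOVA or the GLM is decisive. A plan with one threshold for everything and no deciding test leaves that choice to the analyst, and stating it costs only a few words.

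The ambiguity and the missing deciding test stand. Three things limit them:

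- The rates of 11.6–16.0% require that any significant test counts, and the plan states no such rule. Part of the excess would remain if the GLM sentence were perfectly clear.
- The power figures rest on an assumed shift and assumed correlations. They illustrate known properties of the tests and do not show harm in this trial.
- The sentence on position, saturation and cerebral oximetry justifies the choice of device and is not a formal objective. Introductory text was removed before review, so the absence of a primary outcome or deciding test is established only for the text available.

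Naming a deciding test for rScO2 and cFOE alone would leave oximetry without one. It would also leave two deciding outcomes, so 5% would hold per outcome and not for the overall conclusion about position.

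**Conclusion.** No change to the plan is needed. The section leaves a detail unwritten: which time and test carry the conclusion, and whether the interaction is run for two-time outcomes. It prescribes no wrong method. Every test listed holds its level when used alone (4.8–5.2% in simulation), and the methods needed to compare positions are already named. With two times, the interaction is a one-way ANOVA on the change, so Kruskal-Wallis on that change is available from the same list if normality fails.

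An analyst can fill the gap sensibly by comparing positions at each recorded time or through the GLM main effect, treating the interaction as supporting and the within-infant tests as descriptive, and reporting all position tests. The document is written in the past tense. If results have been seen, a deciding test named now would be post hoc and would not restore error control.

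The size, if every significant test were counted, is about 12–13% per two-time outcome and 12.8–16.0% per three-time outcome, against 5%. This assumes 15 per group, normal data, compound symmetry and correlations of 0.3–0.9. It reflects testing at several times plus the interaction, not the unclear sentence alone.
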